IMV	Institut für Medizinische Virologie in Zürich
ISO	International Organisation for Standardisation
ITT	Intention to treat
MD	Medical Device
MedDO	Medical Device Ordinance (in German: MepV, in French: ODim)

PI	Principal Investigator
RBD	Receptor binding domain
RECORD	REporting of studies Conducted using Observational Routinely-collected Data
SARS-CoV-2	Severe acute respiratory syndrome coronavirus 2
SDV	Source Data Verification
SHCS	Swiss HIV Cohort Study
SOP	Standard Operating Procedure
SPC	Summary of product characteristics
SPIRIT	Standard Protocol Items: Recommendations for Interventional Trials
STCS	Swiss Transplant Cohort Study
SUSAR	Suspected Unexpected Serious Adverse Reaction
TMF	Trial Master File

STUDY SYNOPSIS

Controlled trials to assess approved SARS-CoV-2 vaccines in immunocompromised patients: Third sub-protocol for an observational study comparing benefits and potential risks of the newly approved bivalent SARS-CoV-2 vaccines

Brief Title: Immunocompromised Swiss Cohorts Based Trial Platform, Acronym: COVERALL (COrona VaccinE tRiAL pLatform) bivalent

Rationale: Since January 12, 2021 two mRNA based vaccines against SARS-CoV-2 by Pfizer-BioNTech (Comirnaty®) and by Moderna (COVID-19 mRNA Vaccine Moderna®) have been licensed in Switzerland and roll-out of vaccines has started.

We have set up a COrona VaccinE tRiAL pLatform (COVERALL) nested into the existing prospectively collected data structure of the Swiss HIV Cohort Study (SHCS) and the Swiss Transplant Cohort Study (STCS). Within the frame of a first sub-study (see first sub-protocol) we have assessed in a head-to-head comparison the efficacy of BNT162b2 by Pfizer-BioNTech and mRNA-1273 by Moderna in immunocompromised patients form the SHCS and the STCS. In these patients the antibody response of mRNA-1273 was non-inferior to BNT162b2. Patients living with HIV had in general an antibody response, while a high proportion of transplant recipients had no antibody response. The second substudy found similar results 8 weeks after the 3rd vaccination (i.e. non-inferiority of moderna vaccine; antibody response).

Recently smaller phase II-II studies with bivalent SARS-CoV-2 vaccines have shown superior antibody response against variants that are being monitored such as alpha (B.1.1.7 and Q lineages), beta (B.1.351 and descendent lineages), gamma (P.1 and descendent lineages), delta (B.1.617.2 and AY lineages) and the variant of concern omicron (B.1.1.529, BA.1, BA.1.1, BA.2, BA.3, BA.4 and BA.5 lineages) when compared to the approved monovalent vaccine. We therefore aim to conduct an observational study assessing the immunologic response and safety of the bivalent SARS-CoV-2 vaccines. Currently (23. 9. 2022) the bivalent SARS-CoV-2 vaccine from Moderna (i.e. m-RNA-1273.214) is approved by the Swiss authorities (Swissmedic) and the bivalent SARS-CoV-2 vaccine by Pfizer-BioNTech is under evaluation. Since we do not know when the product from Pfizer-BioNTech will become available, we describe and pre-specify two scenarios for this study.

Scenario 1 (Comparison): In this observational study, we will recruit patients who have received m-RNA-1273.214 by Moderna in the frame of clinical routine. We will start a second arm of our observational study as soon as another bivalent mRNA vaccine (from Pfizer-BioNTech) has been approved by Swissmedic. This will allow for a non-randomized comparison of the 2 bivalent mRNA vaccines.

Scenario 2 (No comparison): In case there is a delay in the approval of the second bivalent mRNA vaccine of more than 3 months after the start of the substudy-3, we will conduct a single arm observational study only (Scenario 2 in Figure 1), because the comparability of the two arms will be increasingly compromised over time.

Objectives and Endpoints:

Aim Scenario 1: To compare immunologic response and safety of the bivalent mRNA-1273.214 vaccine from Moderna among immunocompromised persons (persons living with HIV or kidney or lung transplant recipients) to the immunologic response of immunocompromised persons who received the bivalent mRNA vaccine from Pfizer-BioNTech.

Aim Scenario 2: To assess immunologic response and safety of the bivalent mRNA-1273.214 vaccine among immunocompromised persons (persons living with HIV or kidney or lung transplant recipients).

Objectives:

All objectives and endpoints apply to both scenarios. However, Scenario 1 allows for a comparison of the endpoints between the two vaccines.

1) To assess the efficacy of the bivalent mRNA-1273.214 booster vaccine

2) To evaluate the durability of the bivalent mRNA-1273.214 booster vaccine response: Proportion of participants that show waning of antibody response at 8 weeks and 6 months, respectively, measured by pan-Immunoglobulin (Ig) antibodies

3) To describe the longitudinal T-cell immune response of the bivalent mRNA-1273.214 booster vaccine in a sub-sample of participants: cellular immune response build up and waning

4) To assess the safety of the bivalent mRNA-1273.214 booster vaccine

Endpoints:

Immunological endpoints:

- The proportion of patients with a positive antibody response to SARS-CoV-2 spike (S1) protein receptor binding domain (RBD) in human plasma assessed by the commercial immunoassay Elecsys Anti-SARS-CoV-2 S (Elecsys S) from Roche (1) 4 weeks, 8 weeks, and 6 months after vaccination. An antibody response will be considered to be still sufficient, using the threshold ≥100 units/ml, predicting a protective immune response as indicated by Hall et al. (2), and Khoury and colleagues.(3)
- Geometric mean of quantitative antibodies against RBD at 4 weeks, 8 weeks, and 6 months using Elecsys S test from Roche.
- The proportion of patients with a positive antibody response using SARS-CoV-2 spike (S1) Elecsys S by Roche, using a threshold of ≥0.8 units/ml as defined by the manufacturer at 4 weeks, 8 weeks, and 6 months.
- T-Cell response, using a commercially available Interferon gamma (IFN-γ) release assays (Quant-T-Cell SARS-CoV-2 by Euroimmun and Elecsys® IGRA SARS-CoV-2 by Roche) in a subsample of 60 patients (40 receiving bivalent (Wuhan/BA.1) SARS-CoV-2 mRNA-1273.214 vaccine by Moderna; 20 receiving bivalent (Wuhan/BA.1) SARS-CoV-2 mRNA vaccine by Pfizer-BioNTech) 4 weeks and 6 months after vaccination (sub-sample will be decreased to 40 patients in Scenario 2).

Clinical Endpoints:

- Newly confirmed SARS-CoV-2 infections 4 weeks, 8 weeks, and 6 months after vaccination.
- Newly confirmed symptomatic SARS-COV-2 infection 4 weeks, 8 weeks, and 6 months after vaccination
- Severe COVID-19 infections (requiring hospitalization or leading to death) 4 weeks, 8 weeks, and 6 months after vaccination

Safety endpoints

- Vaccine-related adverse events 4 weeks after vaccination
- Serious adverse events 4 weeks, 8 weeks, and 6 months after vaccination

Overall Design:

Observational study extension conducted within our trial-platform (COVERALL) nested in two national cohorts.

Number of Participants enrolled:

Since our trial platform is nested within two national cohort studies (SHCS and STCS), we have the possibility to identify and invite cohort patients who will receive the new bivalent mRNA Sars-CoV-2 vaccine in the frame of clinical routine. We plan to enrol the following number of individuals:

Scenario 1:

160 patients receiving bivalent (Wuhan/BA.1) SARS-CoV-2 mRNA-1273.214 vaccine by Moderna

- kidney transplant recipients (n=30)
- lung transplant recipients (n=30)
- people living with HIV with CD4 cell counts below 350 cells/ μ L (n=50)
- people living with HIV with CD4 cell counts of \geq 350 cells/µL (n=50)

AND

80 patients receiving bivalent (Wuhan/BA.1) SARS-CoV-2 mRNA vaccine by Pfizer-BioNTech

- kidney transplant recipients (n=10)
- lung transplant recipients (n=10)
- people living with HIV with CD4 cell counts below 350 cells/µL (n=30)
- people living with HIV with CD4 cell counts of \geq 350 cells/µL (n=30)

Sub-sample: A sub-sample of 60 patients will be selected (n=40 bivalent mRNA-1273.214 vaccine by Moderna; n=20 bivalent SARS-CoV-2 mRNA vaccine by Pfizer-BioNTech) for whom we will assess the T-Cell response, measured using the Quant-T-Cell SARS-CoV-2 by Euroimmun and Elecsys® IGRA SARS-CoV-2 by Roche. For this sub-sample we aim to prioritize patients which are at higher risk for a low immune response (i.e. solid organ transplant recipients and people living with HIV wit CD4 counts below 350 cells/µL so that we can include from each of the above groups 10 patients who received bivalent mRNA-1273.214 and 5 who received bivalent SARS-CoV-2 mRNA vaccine by Pfizer-BioNTech).

Scenario 2:

160 patients receiving bivalent (Wuhan/BA.1) SARS-CoV-2 mRNA-1273.214 vaccine by Moderna

- kidney transplant recipients (n=30)
- lung transplant recipients (n=30)
- people living with HIV with CD4 cell counts below 350 cells/µL (n=50)
- people living with HIV with CD4 cell counts of \geq 350 cells/µL (n=50)

Sub-sample: A sub-sample of 40 patients will be selected for whom we will assess the T-Cell response (10 from each of the groups listed above).

Biological Sample and health related data Collection and Duration:

Participants of the Swiss HIV Cohort Study (SHCS) and Swiss Transplant Cohort Study (STCS) with informed consent and no exclusion criteria will be included. At day 0 patients will provide a baseline blood sample and will receive the third SARS-CoV-2 vaccine in the frame of clinical routine. At 4 weeks (± 1 week), 8 weeks (± 2 weeks), and 6 months (± 4 weeks) participants will have a follow up visit in which they provide a blood sample. Clinical outcomes as well as safety outcomes will be assessed.

Study schedule

Assessment	Baseline	4 weeks	8 weeks	6 months
		(± 1 week)	(± 2 weeks)	(± 4 weeks)
Eligibility and consent ^a	Х			
Baseline assessment	Х			
Assessment of monoclonal antibody treatment and flu vaccination	Х	X	Х	Х
Vaccination (mRNA-1273.214 or product by Pfizer-BioNtech) in the frame of clinical routine ^b	Х			
Anti-SARS-CoV-2 S and N antibody tests (Elecsys® Roche)	Х	X	X	x
T-cell test (IFN-γ release assay): Quant-T-Cell SARS-CoV-2 by Euroimmun and Elecsys® IGRA SARS-CoV-2 by Roche Only in sub-sample of 60	х	X		Х
patients (Scenario 1) or 40 patients (Scenario 2)				
Clinical outcomes		Х	Х	Х
Vaccine specific adverse events		Х		
Serious adverse events		Х	Х	х

^a Informed consent can also be given at later time point if bivalent vaccine was already administered in the frame of clinical routine and consent is only referring to blood samples and use of data.

^b Will be administered in the frame of clinical routine based on recommendation from treating physician

2.1 MONITORING INSTITUTION

Central monitoring of data entry into the trial platform and cohort database will be done within the routine procedures by the central and local cohort data managers and the biostatistician responsible as already implemented in sub-protocol 1 and 2.

2.2 DATA SAFETY MONITORING COMMITTEE

Due to the observational nature of this study extension, no data safety moniroring committee will be used.

3. ETHICAL AND REGULATORY ASPECTS

We refer to the master protocol.

3.1 STUDY REGISTRATION

COVERALL is registered with the U.S. National Institutes of Health (www.clinicaltrials.gov) under NCT04805125. The current registration will be adapted to implement the proposed trial extension. All sub-protocols are freely available on https://clinicaltrials.gov/ct2/show/NCT04805125. This extension will also be registered with the Koordinationsstelle Forschung am Mensch (kofam).

3.2 CATEGORISATION OF STUDY

This substudy is an observational extension (HFV2) in the Category A. This sub-study will assess patients blood sample after routine vaccination for immune response against SARS-CoV-2. Of note, the first study within out trial platform (sub-protocol 1) was an interentional study (klinV), while also substudy-2 (sub-protocol 2) was an observational study (HFV2).

3.3 COMPETENT ETHICS COMMITTEE (CEC)

We refer to the master protocol.

3.4 COMPETENT AUTHORITIES (CA)

We refer to the master protocol.

3.5 ETHICAL CONDUCT OF THE STUDY

We refer to the master protocol.

3.6 DECLARATION OF INTEREST

We refer to the master protocol.

3.7 PATIENT INFORMATION AND INFORMED CONSENT

We refer to the master protocol.

3.8 PARTICIPANT PRIVACY AND CONFIDENTIALITY

We refer to the master protocol.

3.9 EARLY TERMINATION OF THE STUDY

The Sponsor-Investigator may terminate the sub-study 3 prematurely according to certain circumstances, for example:

- ethical concerns,
- insufficient participant recruitment,
- when the safety of the participants is doubtful or at risk,

• alterations in accepted clinical practice that make the continuation of this extension study unwise

3.10 PROTOCOL AMENDMENTS

We refer to the master protocol.

4. BACKGROUND AND RATIONALE

4.1 BACKGROUND AND RATIONALE

We have set up a COrona VaccinE tRiAL pLatform (COVERALL) nested into the existing prospectively collected data structure of the Swiss HIV Cohort Study (SHCS) and the Swiss Transplant Cohort Study (STCS), according to an adaptive trial **master protocol** (4). Within the frame of a **first sub-study** we have assessed in a head-to-head comparison the efficacy of BNT162b2 by Pfizer-BioNTech and mRNA-1273 by Moderna in immunocompromised patients form the SHCS and the STCS (5). In these patients the antibody response of mRNA-1273 was non-inferior to BNT162b2. Patients living with HIV had in general an antibody response, while a high proportion of transplant recipients had no antibody response. The **second sub-study** found similar results 8 weeks after the 3rd vaccination (i.e. non-inferiority of moderna vaccine; antibody response; *manuscript in preparation*).

The currently used SARS-CoV-2 vaccines were developed targeting the SARS-CoV-2 wild type and show limited efficacy against newer SARS-CoV-2 variants of concern. Hence, Moderna has developed a new bivalent booster vaccine based on variant spike sequences (Wuhan/Omicron BA.1). In a recent study this newly developed bivalent mRNA-1273.214 vaccine showed also a potent neutralizing antibody response against Omicron subvariants and a superior antibody response against alpha, beta, gamma, delta and omicron variants when compared to the approved monovalent vaccine mRNA-1273 Spikevax (6). Similarly, Pfizer-BioNTech has developed a bivalent mRNA vaccine (Wuhan/Omicron BA.1) with promising results (7, 8). Currently, evidence on the efficacy and safety of bivalent mRNA-vaccines in immunocompromised persons is very limited.

Hence, we propose a **third sub-study** of our COVERALL study assessing the humoral and cellular immune response, clinical and safety outcomes of the bivalent mRNA-vaccines (Wuhan/Omicron BA.1) in patients from the SHCS and STCS who have received at least three monovalent m-RNA SARS-CoV-2 vaccinations by either Moderna or Pfizer-BioNTech. Little is known about the cellular (T-cell mediated) immune response for these bivalent vaccines. Evidence from previous mRNA vaccine studies has shown inconsistent patterns between humoral and cellular response, especially among solid organ transplant recipients (9-11).

We propose to conduct an observational study, with two possible scenarios, dependent on how soon the second bivalent mRNA SARS-CoV-2 vaccine from Pfizer-BioNTEch will become available. Independently, we will start the study with the bivalent mRNA vaccine from Moderna which has already been approved by Swissmedic, being the first bivalent mRNA vaccine available in Switzerland. We will start a second observational arm with the bivalent mRNA vaccine from Pfizer-BioNTech, as soon as it has been approved by Swissmedic. This will allow a non-randomized comparison of the 2 bivalent mRNA vaccine s (Scenario 1 in Figure 1). In case the approval of Pfizer-BioNTech's bivalent mRNA vaccine comes later than than 3 months after study start, we will not open this second observational arm because the non-randomized comparability of the two arms will be too compromised due to time difference (Scenario 2 in Figure 1).

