7.6 ASSIGNMENT TO STUDY GROUPS

Since this is an observational study extension, we will not do any active assignment. Participants will receive the bivalent vaccine which they are given during routine practice. We will implement monitoring reports so capture how many patients from which sub-group are already participating. When the required sample size is reached for a specific sub-group investigators will be informed to stop recruitment for this sub-group of patients.

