13.3.2 Analyses of immunological and clinical outcomes

Descriptive statistics will be used to present immunological and safety outcomes. We will report frequency and percentage with 95% Wald confidene interval (CI) of positive immune response and

geometric mean titer (GMT) with 95% CI. GMT are defiened as the anit-logs of the means and addressed anticipated right-skewness of the data. Safety outcomes will be reported as frequency and percentage with 95% CI. For scenario 1, we will additionally report mean difference in positive response and ratio of GMT between the two bivalent vaccines with 95% CI.

Baseline and demographic characteristics will be summarised overall and -for scenario 1 – by vaccine received.

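### In Scenario 1 the two vaccine arms may overlap little in calendar time, yet the planned between-vaccine estimates make no use of vaccination date

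*Protocol*

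**What the plan says.** All references are to the Protocol (third sub-protocol) unless stated.

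- **Start of the arms.** The Moderna arm begins at once. For the other product, Section 4.1 says: "We will start a second observational arm with the bivalent mRNA vaccine from Pfizer-BioNTech, as soon as it has been approved by Swissmedic".
- **Time limit.** Section 4.1 drops the second arm if approval of the second "bivalent mRNA vaccine comes later than than 3 months after study start, we will not open this second observational arm". The Study Synopsis has the same rule, triggered by a "delay in the approval of the second bivalent mRNA vaccine of more than 3 months after the start of the substudy-3", and gives the reason: "because the comparability of the two arms will be increasingly compromised over time".
- **Quotas.** The Synopsis plans "160 patients receiving bivalent (Wuhan/BA.1) SARS-CoV-2 mRNA-1273.214 vaccine by Moderna" and "80 patients receiving bivalent (Wuhan/BA.1) SARS-CoV-2 mRNA vaccine by Pfizer-BioNTech", each divided into kidney, lung and two HIV groups by CD4 count.
- **Closing rule.** Section 7.6: "When the required sample size is reached for a specific sub-group investigators will be informed to stop recruitment for this sub-group of patients".
- **Comparison.** Section 13.3.2: for Scenario 1, "we will additionally report mean difference in positive response and ratio of GMT between the two bivalent vaccines with 95% CI". No covariate, stratum, vaccination date or restriction to concurrent participants is named. Section 7.2.3, the heading for other bias-reducing methods, has no text under it.
- **Status.** Section 13 calls all analyses exploratory and Section 13.1 states that no hypothesis is tested. Comparing the two vaccines is nevertheless the overall objective of Scenario 1 (Section 6.1).

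**The concern.** The Protocol treats a time difference between the arms as serious enough to cancel the comparison, but it controls only one date, that of approval. Vaccination in the second arm follows approval, no limit is set on how long that arm recruits, and Moderna quotas may already be full by then. Two further provisions can push Moderna dates earlier. Section 7.5 asks sites to recruit people with HIV and low CD4 counts first. Footnote a of the study schedule and Section 10.1.1 admit people vaccinated before the study began, when (at drafting) only the Moderna product was approved.

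Time since the last dose, previous infection and monoclonal antibody use may all differ between people vaccinated at different times, and each may affect the anti-S level. Section 7.4 excludes only acute symptomatic SARS-CoV-2 infection, so previously infected people can enter either arm. If these features drift over the recruitment months, the difference in response and the GMT ratio mix a vaccine effect with a calendar effect. The confidence interval would not show it. A real difference could be hidden, or an apparent one created.

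**Working it through.** **1. The plan's own figure.** Sub-study 3 has no power calculation, so the only figure to reproduce is the size of the convenience sample.

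- Moderna: 30 + 30 + 50 + 50 = 160.
- Pfizer-BioNTech: 10 + 10 + 30 + 30 = 80.
- Total: 240, as stated in Section 13.1.

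**2. How much the arms can overlap.** Accrual times are not given, so those below are assumptions. With constant accrual, let a Moderna quota fill from month 0 to month Tm. Let the second arm recruit from approval at month A (A ≤ 3) for Tp months. Then:

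- concurrent time = max(0, min(Tm, A + Tp) − A);
- share concurrent = that time ÷ Tm for Moderna, ÷ Tp for the second arm;
- gap between mean enrolment dates = A + Tp/2 − Tm/2.

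| A | Tm | Tp | Moderna concurrent | Second arm concurrent | Gap in mean dates (months) |
|---|---|---|---|---|---|
| 3 | 2–3 | 2–3 | 0% | 0% | 2.5–3.5 |
| 3 | 4 | 2–3 | 25% | 33–50% | 2.0–2.5 |
| 3 | 6 | 2–3 | 33–50% | 100% | 1.0–1.5 |
| 2 | 3 | 2–3 | 33% | 33–50% | 1.5–2.0 |
| 1 | 4 | 2–3 | 50–75% | 100% | 0–0.5 |

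Example, second row with Tp = 2: min(4, 5) − 3 = 1 month, so 1/4 = 25% and 1/2 = 50%. Any delay between approval and first use of the second vaccine acts like a larger A.

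**3. What zero overlap would require.** With approval at month 3, a Moderna quota must be full by then. That needs 30/3 = 10 a month for each transplant group, 50/3 = 16.7 a month for each HIV group, and 160/3 = 53.3 a month overall. Overlap has to be judged group by group, since one group can close while another is still open.

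**4. Possible effect on the GMT ratio (illustration only).** Suppose the share with previous infection is x higher in the later arm, previous infection multiplies the titre by k, and the true ratio is 1.00. The crude ratio of second arm to Moderna is then k^x. With x from 0.05 to 0.20 and k from 2 to 5 (assumed), this runs from 2^0.05 = 1.04 to 5^0.20 = 1.38.

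For scale, the 95% interval multiplies and divides the ratio by 10^(1.96 × SD × √(1/160 + 1/80)). With an assumed SD of 0.5 to 1.0 on the log10 scale, the factor is 1.36 to 1.86. The bias could be negligible or about as large as the sampling error.

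**5. Why stratify by patient group as well.** The quotas make transplant recipients 60/160 = 37.5% of the Moderna arm but 20/80 = 25% of the other. A pooled difference in response is shifted by 0.125 × the response gap between HIV and transplant participants. For an assumed gap of 10 to 40 points, that is 1.3 to 5.0 points.

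**The case against.** The strongest reply is that the Protocol is open about the problem. It calls the comparison non-randomised, sets a limit beyond which it will not be made, declares everything exploratory, and tabulates baseline characteristics by vaccine (Section 13.3.2). It also records several relevant variables: monoclonal antibody use at every visit (Section 7.10), S and N antibodies at every visit (Section 10), and earlier vaccinations by month and year (Section 11.1.2). All of this stands, and no error rate or power statement is wrong. But disclosure does not change the estimate, and the plan does not say that the recorded variables will be used in it.

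A second reply is that an unadjusted comparison is inferred from silence. That is fair: Section 13.3.2 does not use the word. Sections 13.3.1 and 13.4 defer to the master protocol, which is not among the documents reviewed. Section 13.3.2, however, sets out this analysis itself and makes no such referral. Section 7.6 also does not say whether sub-groups are counted per vaccine; the Synopsis lists the quotas that way.

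A third reply is that little overlap needs late approval and quick Moderna recruitment together. That stands too. Section 7.5 says fewer than 5% of people with HIV have CD4 counts below 350, so 16.7 a month in that group may be hard to reach.

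Three stronger readings might be inferred, and none is supported:

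- **That the arms will not overlap.** The rules permit this but do not make it happen, as the table shows.
- **That half of the infection follow-up is non-concurrent**, from 3 months of lag over 6 months of follow-up. This ratio describes two people vaccinated 3 months apart. It is not a maximum, because the second arm may enrol later than approval. It is not a bias either, and Section 13.3.2 specifies no between-vaccine infection estimate.
- **That counting the 3 months between first vaccinations would cure the problem.** Moderna quotas could still fill before the second arm's first participant.

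**Conclusion.** The point holds as a risk that the plan leaves uncontrolled. Followed as written, Sections 4.1, 7.6 and 13.3.2 can produce between-vaccine estimates confounded with calendar time, and the only safeguard is the rule for opening the second arm. In the scenarios tabulated, overlap runs from none to the whole second arm. All of these rest on assumed accrual. The GMT ratio range of 1.04 to 1.38 rests on assumed drift in previous infection and its assumed effect on titre, so it shows scale and is not a prediction. The matter deserves a change because the comparison is Scenario 1's overall objective and most of the data needed for a better estimate are already planned. It does not affect Scenario 2, which has a single arm.

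**What to change.** In Section 13.3.2, for Scenario 1:

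1. Keep the crude difference in response and the crude GMT ratio, labelled as descriptive.
2. Pre-specify a between-vaccine estimate stratified by the four patient groups and adjusted for vaccination date and time since last dose, plus baseline S titre and N status where a baseline sample exists.
3. Add a sensitivity analysis limited to participants vaccinated in the calendar period common to both arms.
4. Where a patient group has no calendar overlap, report the arms side by side without a contrast. Adjustment cannot replace this step: with no overlap, vaccine and date cannot be separated, and with very little overlap the adjusted estimate is mostly extrapolation.

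The change is to analysis wording and needs no new visits or samples. It has three costs. Intervals will be wider. The transplant strata will be thin, since the second arm plans only 10 kidney and 10 lung recipients and restriction to the shared period may leave fewer. Baseline adjustment will be incomplete, because people vaccinated before study start have no baseline sample (Section 10.1.1). The number left out of each adjusted estimate should be reported with it.
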